## 2.1.2. Visit Windows

For immunogenicity summaries and tabulations per time point, assessments will be allocated to an analysis visit based on the planned visit as captured in the CRF. Visits that are out of the protocol-defined visit windows (Table 2 below) will not be included in the immunogenicity summaries and tabulations per timepoint. However, they may be included in sensitivity analyses.

**Table 2: Visit Windows for Immunogenicity Analysis**

Analysis time point label (Relative to Day 1)	Target day	Window of target day (days)
Day 1	1	( $-\infty$ , 1]
Day 15	15	[12, 22]
Day 85	85	[71, 99]
Day 183	183	[169, 197]

## 2.2. Pooling Algorithm for Analysis Centers

Data will be pooled across the different centers.

## 2.3. Analysis Sets

Vaccination assignment will follow the as treated principle.

### 2.3.1. Full Analysis (FA) set

The FA set will include all participants who were randomized and received the study vaccine, regardless of the occurrence of protocol deviations. All safety and participant information analyses will be based on the FA set.

### 2.3.2. Per-Protocol Immunogenicity (PPI) set

The PPI set will include all participants who were randomized and received the study vaccine, and for whom immunogenicity data are available, excluding participants with major protocol deviations expecting to impact the immunogenicity outcomes.

The analysis of all immunogenicity endpoints will be based on the PPI set. As a sensitivity analysis, key immunogenicity tables will also be based on the FA set.

## 2.4. Definition of Subgroups

No subgroup analysis is planned for this study.

## 3. INTERIM ANALYSIS AND DATA MONITORING COMMITTEE REVIEW

An internal Data Review Committee (DRC) will be commissioned for this study to discuss any safety issues and any situation meeting a specific study vaccination pausing rule (CTP Sections 9.6 and 7.3). Planned data reviews of the DRC are specified in CTP Section 4.1. The role and responsibilities of the internal DRC are detailed in the DRC Charter. The DRC analyses will follow the same statistical methods described in this SAP. A separate DPS document has been provided to describe specifications of individual tables, listings and figures to be generated in each DRC analysis.

## 4. SUBJECT INFORMATION

Subject information will be analyzed based on the FA set. For each cohort, tables will be presented by vaccine group and overall. Categorical variables will be summarized in frequency tables and continuous variables with descriptive statistics.

### 4.1. Demographics and Baseline Characteristics

The following demographic and baseline characteristics will be summarized.

- Sex (Female/Male)
- Age (years)
- Age categories (years): 60-64, 65-74, 75-84,  $\geq 85$
- Race
- Ethnicity
- Risk level of severe RSV disease (Increased risk / Non-increased risk), as collected (CDC definition)
- Height (cm)
- Weight (kg)
- BMI ( $\text{kg}/\text{m}^2$ )
- BMI categories ( $\text{kg}/\text{m}^2$ ):  $<20$ ,  $20-25$ ,  $25-30$ ,  $\geq 30$

### 4.2. Disposition Information

The number and percentage will be tabulated for subjects that were:

- Screened
- not randomized, not vaccinated
- not randomized but vaccinated
- randomized not vaccinated
- randomized and vaccinated (subjects in the FA set)
- in the PPI set

Number and percentage of subjects who discontinued the study together with the reason(s) for discontinuation will also be tabulated.

The number and percentage of subjects per study phase and period will also be tabulated.

### 4.3. Protocol Deviations

Major protocol deviations will be tabulated.

#### **4.4. Concomitant Medications**

The analysis of concomitant therapies will be done using the World Health Organization (WHO) drug coded terms.

There will be special attention to any systemic use of analgesics/antipyretics, administered during 8 days following each vaccination (00:00 of day of vaccination + 7 days). The following CMCLASCD (ATC/DD codes) will be used for this: N02A (OPIOIDS) and N02B (OTHER ANALGESICS AND ANTIPYRETICS), M01A (ANTIINFLAMMATORY AND ANTIRHEUMATIC PRODUCTS, NON-STEROIDS) and M01B (ANTIINFLAMMATORY/ANTIRHEUMATIC AGENTS IN COMBINATION). The classes will be added in a footnote in all related tables and listings.

Concomitant therapies will be reported in each applicable study phase based on their start and stop date. That is, a concomitant therapy will be allocated to each study phase in which it was taken.

If a concomitant therapy records misses components of its start and/or stop dates (day and/or month and/or year):

- In the event of a partial start or stop dates, the concomitant therapy records will be allocated to phases using the available partial information, without imputations. If, for example, only month and year are available, these will be compared to the month and the year of the phases, and the concomitant therapy record will be allocated to the phase(s) where these date parts match. This rule may lead to assignment to multiple phases. The same rule applies for identifying whether a concomitant therapy was administered during 8 days following a vaccination. For example, if the vaccination was administered on the 30th of December 2017 and the concomitant therapy start date is January 2018 (missing day), then the concomitant therapy will be assumed to have started within 8 days of the vaccination.
- In the event of a completely missing start date, the concomitant therapy will be considered as having started before the study.
- In the event of a completely missing end date, the concomitant therapy will be considered as ongoing at the end of the study.

Concomitant therapies will be tabulated per study phase and period.

#### **4.5. Medical History**

Medical history and concomitant diseases will be listed.

## 5. IMMUNOGENICITY

### 5.1. Parameters

The immunogenicity endpoints (primary, secondary and exploratory endpoints) are described in CTP Section 3. The following immunogenicity assays are applicable for this study:

#### **Immunogenicity against RSV:**

##### *Humoral Immune Response*

- Pre-F protein binding antibodies using enzyme-linked immunosorbent assay (ELISA)
- RSV A2 neutralizing antibodies
- Post-F protein binding antibodies (ELISA)\*
- RSV cross-neutralization of B and/or other A strain(s) \*
- Anti-F protein antibody specificity characterization\*
- Nasal immunoglobulin (Ig)A and/or IgG binding to RSV F protein in prefusion and/or postfusion form\*

##### *Cellular Immune Response*

- Antigen-specific T-cell immune responses\*
- Interferon (IFN)- $\gamma$  enzyme-linked immunospot (ELISpot)

#### **Immunogenicity against Ad26:**

- Neutralizing antibodies to Ad26\*

*\* This is an exploratory endpoint, it will only be analyzed if available.*

### 5.2. Handling of Missing and/or Unquantifiable Immune Response Data

Missing immune response data will not be imputed.

Values below the lower limit of quantification (LLOQ) will be imputed based on the type of analysis. For the calculation of the geometric mean titer, values below LLOQ will be imputed to LLOQ/2. While for the calculation of the geometric mean increases, values below LLOQ will be imputed to LLOQ.

For ICS assays (if available), the LLOQ will be used if available and validated. In case no validated LLOQ is available then a provisional cut-off will be provided before database lock. Negative observations will be set to zero before calculating the total cytokine responses or other ICS parameters. For descriptive statistics or graphs on actual values, values below the LLOQ or cut-off will also be imputed to a value of LLOQ/2 or cut-off/2.

Values above the upper limit of quantification (ULOQ) will be imputed to ULOQ.

The LLOQ and ULOQ values per assay will be available in the database.

## 5.3. Immune Response Analysis

Immunogenicity data will be summarized per cohort, vaccine group and timepoint. For a selection of tables, data might be pooled over cohorts.

The primary analysis set for immunogenicity is the PPI set. As a sensitivity analysis, key tables will also be generated based on the FA set to explore the effect major protocol deviations. Depending on their occurrence, this factor might be further explored.

### 5.3.1. Immunogenicity Against RSV

#### 5.3.1.1. Humoral Assays

For humoral assays, N, geometric mean (GMT)§ and corresponding 95% CI of the actual values will be calculated. The fold increases from baseline will be tabulated and graphically presented. *§The mean and corresponding 95%CI will be calculated on the log2-transformed values, and then back-transformed [i.e. 2^mean] and CI [i.e. 2^CI].*

Actual values and fold changes from baseline will be summarized in tables and dot plots, with dots for subject values, and the corresponding geometric mean and 95% CI per time point for each assay. In addition, GMT plots over time, combining the regimens in one graph (without individual subject dots) will also be created.

Ratios of actual values and ratios of fold changes from baseline between humoral assays may also be presented. Subject profiles of the actual values over time will be graphically presented. Reverse distribution curves of the actual values will be provided for selected time points. In the graphs, original values will be displayed on the log2 scale.

A scatterplot of the virus neutralization assay (VNA) versus ELISA will be provided for the most important time points. In these scatterplots the actual values will be shown, even if they are below the LLOQ, but the LLOQ cut-off will be visualized in the graph per assay if some values are below LLOQ.

To explore the dose-response relationship between pre-F ELISA and different dose levels of the study vaccine, a linear regression model will be fitted for each timepoint separately, using data of the active groups of Cohort 1, with the log transformed pre-F ELISA titers at the considered timepoint as dependent variable, the number of titration steps as independent variable, and the GMT of pre-F ELISA of the Ad26/protein pre-F RSV vaccine ( $1 \times 10^{11}$  vp/150 µg) at the considered timepoint as a fixed intercept. The regression slope and 95% one-sided lower confidence limit for the slope will be calculated.

The following linear model will initially be fitted for the active groups of Cohort 1 but may be extended in a later stage with data of the active groups of Cohorts 2 and 3. A similar model may be fitted as well for other assays:

$$\log_2(\text{pre-F ELISA}_{\text{timepoint}}) = \text{GMT pre-F ELISA}_{\text{Ad26/protein } (1 \times 10^{11} \text{ vp}/150 \mu\text{g}), \text{timepoint}} + \text{slope} \cdot \# \text{titration steps} + \text{error}$$

Depending on the model fit, other models (such as, log-linear models or EMAX models) may be explored as well.

Other exploratory immunogenicity parameters maybe analyzed at the discretion of the sponsor.

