1.3. Schedule of Activities

1.3.1. Cohort 1

Clinic Visit #	1	2 ^a	3	4 ^a	5	6	Early Exit ^b
Visit Timing	Vac	Vac + 7 d	Vac + 14 d	Vac + 28 d	Vac + 84 d (3 m)	Vac + 26 wk (6 m)	
Visit Day(s)	1	8	15	29	85	183	
Visit Window		±2 d	-3 d/+7 d	±7 d	±14 d	±14 d	
Visit Type	SCREENING AND STUDY VACCINATION	Safety	Safety and Immunogenicity	Safety	Safety and Immunogenicity	Safety and Immunogenicity	Early Exit
Written informed consent ^c	●						
Inclusion/exclusion criteria	●						
Demographics	●						
Medical history/prestudy therapy ^d	●						
Physical examination ^e	●		●		●	●	●
Vital signs ^f	●		●		●	●	●
Randomization	●						
Participant diary distribution	●						
Contraindications to vaccination ^g	●						
Cellular immunity sample, mL	● 50		● 50		● 50	● 50	● 50
Humoral immunity sample, mL	● 10		● 10		● 10	● 10	● 10
Nasosorption sample	●		●		●	●	●
Vaccination	●						
30-minute postvaccination observation ^h	●						
Solicited AE recording ⁱ	- - Continuous - -						●
Unsolicited AE recording ^j	- - - Continuous - - -						●
SAE recording ^k	- - - Continuous - - -						●
Concomitant therapy ^l	- - - Continuous - - -						●
Participant diary review of solicited AEs by study-site personnel ^m		●					
Blood draw volumes							
Approximate daily blood draw, mL	60	-	60	-	60	60	60
Approximate cumulative study blood draw, mL	60	60	120	120	180	240	-

d = day; m = month; Vac = vaccination; wk = week.

❶ prevaccination; ❷ pre- and postvaccination; ❸ if the early exit visit is within 8 days after vaccination; ❹ blood samples for immunogenicity will only be taken if the early exit visit is at least 14 days after the previous immunogenicity blood draw; ❺ if the early exit visit is within 7 days after vaccination; ❻ if the early exit visit is within 28 days after vaccination; ❻ at the discretion of the investigator (based on health status of the participant).

- a. Can be electronic (eg, e-mail, text messages) or by phone.
- b. An early exit visit will be conducted for those participants who are unable to continue participation in the study and withdraw from the study before Day 183, but who do not withdraw consent. Participants who wish to withdraw consent from participation in the study will be offered an early exit visit (prior to formal withdrawal of consent).
- c. Signing of the ICF should be done before any study-related activity.
- d. Prestudy therapies administered up to 30 days before vaccination must be recorded.

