The planned primary and final analyses of all cohorts are detailed in Section 9.5. The primary analyses of Cohorts 2 and 3 will be combined.

After vaccination with study vaccine on Day 1, participants will remain under observation at the study site for a minimum of 30 minutes for presence of any acute reactions and solicited events, or longer if deemed necessary by the investigator. Any unsolicited and solicited local (injection site) or systemic AEs will be documented by the study-site personnel following this observation period. Participants will be given a thermometer, ruler, and a daily assessment (participant) diary with instructions for the proper recording of events. Each participant will record solicited local and systemic AEs and body temperature in the participant diary, beginning on the evening of the vaccination day and daily for 7 days after vaccination. Body temperature should be taken at approximately the same time each day. Study-site personnel will collect and review participant diary information and confirm the entries at the next visit.

The reporting periods of AEs, SAEs, and special reporting situations are detailed in Section 8.3. Reporting periods for concomitant therapy are outlined in Section 6.5.

Nasosorption samples using synthetic absorptive matrix (SAM) strips will be collected on Day 1 (prevaccination) and at 14 days and 3 and 6 months after vaccination (Section 8.1). Blood

samples to assess humoral and cellular immune responses will be collected on Day 1 (prevaccination) and at 14 days and 3 and 6 months after vaccination (Section 8.1). Clinical safety laboratory blood samples (Cohorts 2 and 3 only) will be collected at the screening visit, on Day 1 (prevaccination), and at 7 days after vaccination (or at the early exit visit if this visit is within 8 days after vaccination and the participant discontinues the study without withdrawing consent) (Section 8.2.3). Participant safety throughout the study will further be evaluated via physical examinations and vital signs (Sections 8.2.1 and 8.2.2, respectively).

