9.4.2. Immunogenicity Analyses

No formal statistical testing of immunogenicity data is planned. Immunogenicity data will be analyzed descriptively by cohort and group. In addition, for a selection of tables, data may be pooled over cohorts.

Descriptive statistics (eg, geometric mean and 95% confidence interval [CI] for ELISA and VNA data; median and quartiles for ELISpot) will be calculated for continuous immunologic parameters at all timepoints. For the humoral assays, geometric mean fold rises from baseline and corresponding 95% CIs might additionally be calculated. Baseline is considered as the last available assessment before vaccination. Graphical representations of immunologic parameters will be made as applicable.

Frequency tabulations will be calculated for discrete (qualitative) immunologic parameters as applicable.

To explore the dose-response relationship between preF ELISA and different dose levels of the Ad26/protein preF RSV vaccine, a linear regression model will be fitted for each timepoint separately, using data of the active groups of Cohort 1, with the log-transformed preF ELISA titers at the considered timepoint as dependent variable, the number of titration steps as independent variable, and the geometric mean titer (GMT) of preF ELISA of the Ad26/protein preF RSV vaccine (1×10^{11} vp/150 μ g) at the considered timepoint as a fixed intercept.

The linear model $\log_2(\text{preF ELISA}_{\text{timepoint}}) = \text{GMT preF ELISA}_{\text{Ad26/protein preF RSV vaccine } (1 \times 10^{11} \text{ vp/150 } \mu\text{g}), \text{timepoint}} + \text{slope} \times \# \text{titration steps}$ will initially be fitted for the active groups of Cohort 1 but may be extended in a later stage with data of the active groups of Cohorts 2 and 3. A similar model may be fitted as well for other assays.

Depending on the model fit, other models (eg, log-linear models or EMAX models) may be explored as well.

The incidence of neutralizing antibodies to Ad26 might be summarized for participants who are positive for antibodies to Ad26.

Other immunogenicity analyses may be performed to further characterize the immune responses that are generated.

The primary analysis set for the immunogenicity analysis is the PPI set. As a sensitivity analysis, key tables may also be based on the FAS.

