## 2. GENERAL ANALYSIS DEFINITIONS

### 2.1. Study Phases

A baseline (or reference) value will be defined as the value of the last available assessment prior to the vaccination on Day 1.

Study day or relative day is defined as follows:

- Study Day = visit date – date of Day 1 + 1; if visit date  $\geq$  date of Day 1 (date of first vaccination).
- Study Day = visit date – date of Day 1; if visit date  $<$  date of Day 1 (date of first vaccination).

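### The Cohort 1 dose-response regression leaves out the Day 1 preF ELISA titer, giving up precision that could be had at almost no cost

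*SAP*

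**What the plan says.** SAP section 5.3.1.1 describes one dose-response model. It is fitted at each timepoint to Groups 1 to 4 and has this form: "with the log transformed pre-F ELISA titers at the considered timepoint as dependent variable, the number of titration steps as independent variable". Its intercept is fixed at the GMT of the 1x10^11 vp/150 µg group at that timepoint. Protocol section 9.4.2 says the same: "with the log-transformed preF ELISA titers at the considered timepoint as dependent variable, the number of titration steps as independent variable". The displayed equation has an intercept, a slope on titration steps and an error term, and nothing else. The output is set out as follows: "The regression slope and 95% one-sided lower confidence limit for the slope will be calculated".

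The baseline titer is available. The Cohort 1 schedule (Protocol section 1.3.1) has a row "Humoral immunity sample, mL" with a draw at the vaccination visit, and Protocol section 4.1 places that draw before vaccination. SAP section 2.1 defines baseline: "A baseline (or reference) value will be defined as the value of the last available assessment prior to the vaccination on Day 1". SAP section 5.3.1.1 already uses it: "The fold increases from baseline will be tabulated and graphically presented".

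**The concern.** Variation in the post-vaccination titer that the Day 1 titer would explain stays in the residual and widens the confidence limit for the slope. Because dose is randomized in Cohort 1, baseline is independent of dose in expectation, so leaving it out does not bias the slope. The question is one of efficiency.

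This is the only model the plan commits to for the Cohort 1 primary objective. Its slope SE is the sole basis for the Cohort 1 immunogenicity sample size (Protocol section 9.2.1). The trial is meant to inform the lower release limit (Protocol section 2.1). With no hypothesis test planned, precision is what the design has to offer. The fold-increase tables summarise groups and give no slope. The optional log-linear or EMAX models change the curve shape and do not add a covariate.

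**Working it through.** **Inputs from the documents** (Protocol section 9.2.1): SD on the log2 scale 1.3 at Day 15 and 1.1 at Day 183; 50 per arm less 10% exclusions, so n = 45; four dose levels.

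**Assumptions:** steps are coded x = 0, 1, 2, 3, and the intercept is read as the log2 of the Group 1 GMT. The within-group correlation r between log2 Day 1 and log2 post-vaccination titer is not in the documents, so 0 to 0.7 is used as a range.

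**The plan's own figure.** With the intercept treated as known, SE = SD / sqrt(n x sum x^2).
- n x sum x^2 = 45 x 14 = 630.
- Day 15: 1.3 / sqrt(630) = 0.0518, which matches the stated 0.052.
- Day 183: 1.1 / sqrt(630) = 0.0438, which does not match the stated 0.040. That is a separate point.

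**Sampling SE of the unadjusted slope.** The Group 1 GMT is itself estimated from 45 participants, so the slope varies more than the nominal SE says.
- Planned anchor: SD x sqrt(1/630 + (270/630)^2/45) = SD x 0.0753, giving 0.0979 (Day 15) and 0.0828 (Day 183). Here 270 = 45 x (0+1+2+3).
- Estimated intercept: SD / sqrt(45 x 5) = SD / 15, giving 0.0867 and 0.0733.

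**Effect of adjusting for baseline.** The residual SD is multiplied by sqrt(1 - r^2), and the SE with it.

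| | r = 0 | r = 0.3 | r = 0.5 | r = 0.7 |
|---|---|---|---|---|
| sqrt(1 - r^2) | 1 | 0.954 | 0.866 | 0.714 |
| Day 15, anchored | 0.0979 | 0.0934 | 0.0848 | 0.0699 |
| Day 183, anchored | 0.0828 | 0.0790 | 0.0717 | 0.0591 |
| Day 15, estimated intercept | 0.0867 | 0.0827 | 0.0751 | 0.0619 |
| Day 183, estimated intercept | 0.0733 | 0.0700 | 0.0635 | 0.0524 |

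The variance falls by r^2. At r = 0.5 this is worth 45 / 0.75 = 60 participants per arm instead of 45.

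**On the titer scale.** Three steps below 1x10^11 vp, the one-sided 95% lower limit of the GMT ratio is the point estimate times 2^(-3 x 1.645 x SE). At Day 15:
- anchored: 0.72 unadjusted; 0.73 / 0.75 / 0.79 at r = 0.3 / 0.5 / 0.7;
- estimated intercept: 0.74 unadjusted; 0.75 / 0.77 / 0.81;
- nominal SE of 0.0518: 0.84.

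A correctly computed adjusted limit is therefore wider than the one the plan would print, unless r exceeds sqrt(1 - (0.0518/0.0867)^2) = 0.80 (estimated intercept) or sqrt(1 - (0.0518/0.0979)^2) = 0.85 (anchored).

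**Simulation.** 8,000 trials per setting at Day 15, with true slope -0.30 and assumed log2 baseline mean 8 and SD 1.1, at r = 0 / 0.3 / 0.5 / 0.7:
- anchored, unadjusted SE: 0.0995 / 0.0978 / 0.0970 / 0.0962;
- anchored, baseline centred on the Group 1 mean: 0.0996 / 0.0937 / 0.0842 / 0.0693, with mean slope -0.30 throughout;
- coverage of the adjusted lower limit, with an SE that allows for the estimated Group 1 GMT: 95.0% / 95.0% / 95.3% / 95.2%.

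Two simpler ways of adding baseline to the fixed-intercept model do worse in simulation:
- Uncentred baseline biases the slope, to -0.36 / -0.40 / -0.44 at r = 0.3 / 0.5 / 0.7 against a true -0.30.
- Centring on the overall mean and keeping the unadjusted Group 1 GMT gives an SE of only about 0.092 at r = 0.5 and 0.086 at r = 0.7.

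**The case against.** The strongest reply is that nothing here is wrong. An unadjusted regression in a randomized cohort is valid, no test is planned, and the protocol judges its precision adequate for an exploratory trial. The benefit rests on a correlation the documents do not supply, and the range starts at zero. No threshold is set for the slope or the GMT ratio, so no decision can be shown to change. Protocol section 9.4.2 also permits further immunogenicity analyses, so an adjusted slope could be run without an amendment.

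All of that stands, and it limits the point to an optional improvement. A general permission, however, is not a commitment. An adjusted slope chosen after the sponsor is unblinded to Cohort 1 would look data-driven.

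A second reply is that the fixed-intercept SE is the larger problem. This also stands. If baseline is added but the plan's SE method is kept, then at r = 0.5 the printed SE is about 0.045 against a true 0.085, and the lower limit covers about 81%, the same as without adjustment. Baseline adjustment cannot stand in for correcting that SE.

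Third, the careless version introduces bias where there was none. That is a reason to write the model out in full.

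**Conclusion.** The point holds as a low-cost precision improvement. The Day 1 titer is collected and defined but absent from the regression, and leaving it out costs precision only. Compared like for like, the slope SE would be 5%, 13% or 29% smaller at r = 0.3, 0.5 or 0.7, and unchanged at r = 0.

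This rests on the assumed r, equal SDs across doses as the protocol assumes, 45 evaluable per arm, and exclusions from the per-protocol set that do not depend on baseline titer differently by dose. Nothing in the documents suggests that they would.

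**What to change.** Before Cohort 1 is unblinded, add to SAP section 5.3.1.1:

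- **Covariate.** Include log2 Day 1 preF ELISA titer at each timepoint in the Cohort 1 active groups, and keep the unadjusted fit as supportive.
- **If the planned anchor is kept.** Add beta x [log2(Day 1 titer) - Group 1 mean log2(Day 1 titer)]. Take the Group 1 GMT and the Group 1 baseline mean from the same participants as the adjusted fit. Use an SE that allows for the Group 1 GMT being estimated.
- **If the sponsor separately decides to estimate the intercept.** Add log2(Day 1 titer) directly.
- **Values below LLOQ.** SAP section 5.2 has two rules, LLOQ/2 for geometric mean titers and LLOQ for geometric mean increases. Name the first for the covariate: "For the calculation of the geometric mean titer, values below LLOQ will be imputed to LLOQ/2".
- **Missing Day 1 titer.** Leave these participants out of the adjusted fit only.
- **Comparison.** Judge the gain against the unadjusted fit with the same SE method, not against the nominal 0.052.

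The cost is SAP text and programming for the centring and the SE, plus one of about 178 residual degrees of freedom. No new samples or assays are needed. Losing a share m of participants inflates the SE by 1/sqrt(1 - m), so the gain is cancelled once m exceeds r^2: 9%, 25% or 49% at r = 0.3, 0.5 or 0.7.

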9.2. Sample Size Determination

9.2.1. Immunogenicity (Cohort 1)

The primary objective of Cohort 1 is to explore the dose-response relationship of humoral immune responses (as measured by preF ELISA) induced by different dose levels of the Ad26/protein preF RSV vaccine.

Assuming:

- 10% of exclusions (eg, drop-outs, missing samples, and major protocol deviations impacting immunogenicity data)
- a standard deviation on the \log_2 scale of the preF ELISA of 1.3 on Day 15 and 1.1 on Day 183 for all dose levels
- 4 dose levels

The linear model $\log_2 (\text{preF ELISA}_{\text{timepoint}}) = \text{GMT preF ELISA}_{\text{Ad26/protein preF RSV vaccine (1x10}^{11} \text{vp/150 }\mu\text{g),timepoint}} + \text{slope} \times \# \text{titration steps}$ provides a standard error for the slope of 0.052 on Day 15 and 0.040 on Day 183 with 50 participants per arm. This is deemed sufficient for this exploratory study.

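### The Cohort 1 dose-response model treats an estimated GMT as a known intercept, so the slope's SE is about half its true size and the nominal 95% one-sided lower limit covers about 81%

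*SAP*

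**What the plan says.** SAP 5.3.1.1 and Protocol 9.4.2 specify the same model. At each timepoint separately, and "using data of the active groups of Cohort 1", log-transformed pre-F ELISA titer is regressed on the number of titration steps. In the protocol, the GMT of the 1×10^11 vp/150 µg vaccine enters "at the considered timepoint as a fixed intercept". The SAP enters it the same way and adds a confidence limit: "at the considered timepoint as a fixed intercept. The regression slope and 95% one-sided lower confidence limit for the slope will be calculated". Neither document says that the uncertainty of the GMT is carried into that limit, and neither states in words which participants supply the GMT.

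Protocol 9.2.1 bases the Cohort 1 sample size on this model. It assumes 10% exclusions, four dose levels and a standard deviation on the log2 "scale of the preF ELISA of 1.3 on Day 15 and 1.1 on Day 183 for all dose levels". It concludes that the model "provides a standard error for the slope of 0.052 on Day 15 and 0.040 on Day 183 with 50 participants per arm", and judges this sufficient for an exploratory study. The synopsis repeats these figures.

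**The concern.** A regression line forced through a fixed point has a small slope SE because only the slope is estimated. That SE is valid if the point is truly known. Here the point is itself a sample mean. If it comes out too high or too low by chance, the slope tilts to compensate, and the model's SE does not register this.

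The slope limit comes from the only dose-response model specified for Cohort 1's primary objective; other models may be explored depending on fit. Protocol 2.1 says the study is meant to support refinement of release and stability acceptance criteria, with immunogenicity informing the lower release limit. A lower limit that sits too close to the estimate overstates how well titers are shown to hold up as the dose falls. The precision on which the sample size was called sufficient is also not what the design delivers.

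**Working it through.** **Inputs**
- 50 per active arm with 10% exclusions gives n = 45 evaluable per arm (Protocol 9.2.1).
- The doses 1×10^11, 3.3×10^10, 1.1×10^10 and 3.7×10^9 vp (Protocol Table 2) are threefold dilutions. In log base 3 they lie at 0, 1.01, 2.01 and 3.00, so the steps are x = 0, 1, 2, 3.
- SD on the log2 scale is 1.3 (Day 15) and 1.1 (Day 183).
- The limit is one-sided 95%, so z = 1.645.
- Sums over the four arms: Σx = 45×6 = 270; Σx² = 45×14 = 630; Σ(x − 1.5)² = 45×5 = 225.

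**The plan's own figure**

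With a known intercept, SE = SD/√Σx².
- Day 15: 1.3/√630 = 0.0518, which matches the stated 0.052. A free intercept would give 1.3/√225 = 0.0867, which does not match. The planning SE therefore assumes an intercept without error.
- Day 183: 1.1/√630 = 0.0438, not the stated 0.040. An SD of 1.0 would give 0.0398. This is a separate discrepancy, not caused by the fixed intercept.

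**True sampling variance of the anchored slope**

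Let a be the Group 1 mean of log2 titer. The estimator is

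slope = Σx(y − a)/Σx² = Σxy/Σx² − a·Σx/Σx².

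Group 1 has x = 0 and contributes nothing to Σxy, so the two terms are independent:

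Var(slope) = SD²·[1/Σx² + (Σx/Σx²)²/45] = SD²·[1/630 + (270/630)²/45] = SD²·[0.001587 + 0.004082].

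The omitted second term is 2.57 times the first.

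| | Planned formula | True SE, anchored | SE, free intercept |
|---|---|---|---|
| Day 15 (SD 1.3) | 0.0518 | 0.0979 | 0.0867 |
| Day 183 (SD 1.1) | 0.0438 | 0.0828 | 0.0733 |

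The ratio of reported to true SE is √(14/50) = 0.529, so the true SE is 1/0.529 = 1.89 times the reported one. With equal arms this ratio depends on neither SD nor n, so it applies at every timepoint.

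**Coverage of the one-sided limit**

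Φ(1.645 × 0.529) = Φ(0.870) = 80.8%.

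Simulation with t-based limits (100,000 trials in each of three scenarios) gave 80.8% to 81.0%. At SD 1.3 the empirical SD of the slope was 0.098, against a mean reported SE of 0.0516. Ordinary regression with a free intercept covered 95.0% to 95.1% in the same simulations.

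**Effect on the fold-change scale at Day 15, over three steps**

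The lower limit as a multiple of the point estimate is 2^(−3 × 1.645 × SE):
- as planned: 2^(−0.256) = 0.84
- anchored, with the true SE: 2^(−0.483) = 0.72
- free intercept: 2^(−0.428) = 0.74

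**Sensitivity to the source of the GMT (Day 15, regression on Cohort 1)**

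Replace the 45 in the second variance term by the number m behind the GMT, with 10% exclusions for in-trial groups.

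| GMT source | m | True SE | Coverage |
|---|---|---|---|
| Group 1 | 45 | 0.0979 | 80.8% |
| Groups 1 and 6 | 90 | 0.0783 | 86.2% |
| Groups 1, 6 and 9 | 112.5 | 0.0738 | 87.6% |
| External, assumed 200 participants | 200 | 0.0651 | 90.5% |
| Known without error | – | 0.0518 | 95.0% |

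**The case against.** **The source of the GMT is inferred.** The documents identify the anchor by regimen, not by group. That dose is given in all three cohorts and is also under study in two other trials (Protocol 4.3). Some tables may pool cohorts, and the model itself "may be extended in a later stage with data of the active groups of Cohorts 2 and 3". Of the sources examined, Group 1 alone gives the lowest coverage. This stands as a caveat, but a modest one. The initial fit uses Cohort 1 only, and Protocol 9.5 provides for unblinding Cohort 1 at its own primary analysis. SAP 5.3.1.1 describes the GMT as a back-transformed mean of log2 values in this trial, and no external source is named. The other in-trial sources still give only 86% to 88%, and pooling across separately randomized cohorts would add an assumption of no cohort effect.

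**The analysis is descriptive.** There is no hypothesis, margin or decision rule on the slope. The primary endpoint is the Day 15 titer, and the group GMTs with their confidence intervals are unaffected. No section ties the slope limit to a release threshold. This limits the consequences: no formal decision is reversed. It does not excuse the label, because a limit reported as 95% should cover about 95%, and the planning SE is understated whatever the study's status.

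**A free intercept is not the only remedy.** Carrying the anchor's variance into the limit also restores coverage. If the response plateaus, as the Emax option in the plan allows, a free straight line need not pass through the observed reference GMT. Both points are fair, so either remedy is acceptable.

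**Conclusion.** The plan is wrong as written. If the anchor is the Group 1 GMT, the reported SE is 0.53 of the true one and the nominal 95% one-sided lower limit covers about 81% at every timepoint. Across in-trial sources for the GMT, coverage runs from about 81% to 88%. It reaches 95% only if the GMT has no error. The direction is anti-conservative: over three steps at Day 15 the limit sits at 0.84 of the estimate when it should sit at 0.72. If the line is straight, the Group 1 anchor also gains nothing, since its true SE (0.098) exceeds that of ordinary regression (0.087).

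These figures assume 45 evaluable participants in each active arm, equal SD across doses and a log2 titer linear in titration steps. The ratio and the 81% do not depend on the SD or on the common arm size. The descriptive status of the study moderates the consequences, but this is the model for Cohort 1's primary objective and should be corrected before that analysis.

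**What to change.** In SAP 5.3.1.1 and Protocol 9.4.2 (and the synopsis), take one of two routes:

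1. **Preferred:** fit log2(titer) = intercept + slope × steps with the intercept estimated from the data, and report that slope with its one-sided 95% lower limit. Under linearity, the fold change from the 1×10^11 vp dose is 2^(slope × steps) and needs no anchor. Against a Group 1 anchor the true SE falls by about 11% (0.0867/0.0979 = 0.886).
2. **If the anchor is kept:** name the groups that supply the GMT and compute the slope's SE with the second variance term included.

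In Protocol 9.2.1 and the synopsis, restate the planning SEs. For the free intercept they are 0.087 (Day 15) and 0.073 (Day 183); for a Group 1 anchor they are 0.098 and 0.083. Either set also replaces the Day 183 value of 0.040, which does not follow from the stated SD. The judgement that precision is sufficient should then be made on the restated figures.

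Wherever the anchored equation is retained, write the intercept as log2(GMT). The left side is log2(titer) while the intercept is shown as an untransformed GMT. This is a notation slip that does not affect the SE or coverage.

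The cost is wording and less favourable planning SEs. No participants, samples or visits are added.
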